# 3.6 Treatment Administration and Blinding

### **Treatments Administered**

Study Treatment Name:	Alvelestat 120 mg	Placebo
Dosage Formulation:	Tablet	Tablet

Unit Dose Strength(s) / Dosage Level(s):	4 × 30 mg Alvelestat	4 × 30 mg Placebo				
Route of Administration	Oral	Oral				
Dosing Instructions:	To be taken bid, 12 hour	s apart and with water				
Packaging and Labeling:	Study treatment will be provided in boxes. Each box will contain treatment for 7 days and will be labeled as required per U.S. regulations.					
Manufacturer:	Mereo BioPharma 4 Ltd. London, W1G 0QF, UK	, 1 Cavendish Place,				

This is double-blind study. The investigators, participants, Mereo and NCATS will remain blinded to the study treatment allocation until the end of the study. The randomization list will be kept secured from the study team, investigators, and participants throughout the conduct of the study and until unblinding is authorized by the DCC. The DSMB will be unblinded according to the DSMB charter.

The IWRS will be programmed with blind-breaking instructions. The study blind may be broken for a medical emergency in which the knowledge of the specific blinded study treatment will affect the immediate management of the participant's condition. In this case, the DCC, the NCATS Medical Monitor, and Mereo must be notified within 24 hours after breaking the blind. The date and reason that the blind was broken must be recorded in the source documentation and case report form (CRF), as applicable.

# 3.7 Study Procedures and Flowchart

Study procedures and their timing are summarized in the Schedule of events (SOA) – see Figure 2.

### Figure 2: SCHEDULE OF ACTIVITIES (SOA)

Visit #	Visit 1	Visit 2	Visit 3	Visit 4	Visit 5	Visit 6	Visit 7	Visit 8	Visit 9	Visit 10	Visit 11	Visit 12
Visit Description	Pre- bronch/ Screen	Baseline bronch	Randomize	Safety F/U	Safety F/U	4 week F/U	Safety F/U	8 week F/U	Safety F/U and Pre- bronch	End of study bronch	Study End	Washout End
Week (from randomization)	-4 to 0	-1	0	+1	+2	+4	+6	+8	+10	+11	+12	+16
Randomization			Х									
Baseline history	Х											
Physical exam	Х	Х	Х	Х	Х	Х	Х	Х	Х	Х	Х	Х
Interim history and adverse event recording		х	x	х	х	х	x	x	x	x	х	х
Blood draw (routine/safety)	х			х	х	х	x	x	x		х	х
Blood draw (biomarkers)	х		х			х		х			х	х
Blood (PK)			X@	Х	Х	Х		Х	Х		Х	
Pregnancy test	Х		Х	Х	Х	Х	Х	Х	Х		Х	Х
ECG	Х		X@	Х	Х	Х		Х	Х		Х	Х
Sputum biomarkers	Х										Х	
Spiro- pre and post BD			x			х					х	x
Spiro – post BD	Х								Х			
PROs#			х			Х					Х	Х
Bronchoscopy		Х								Х		
Phone contact		X ( day after)								X ( day after)		
Electronic diary	X		X	X	X	X	X	X	X	X	X	X

\*Patient reported outcomes to include Modified Medical Research Council questionnaire (MMRC), COPD assessment test (CAT), St George Respiratory Questionnaire (SGRQ), San Diego Shortness of Breath Questionnaire; @ pre-dose and between 1 and 2 hours post-dose

# 4 Endpoints

### 4.1 Primary Efficacy Endpoints

Within-individual % change from baseline in plasma desmosine/isodesmosine at end of treatment with MPH966

# 4.2 Primary Safety Endpoints

- 1. Numbers and % of subjects who experience at least 1 treatment-emergent adverse event
- 2. Adverse events of special interest (liver function abnormalities, corrected QT interval/cardiac, infections, and neutropenia)

# 4.3 Secondary Efficacy Endpoints

Blood pharmacodynamic markers of neutrophil activation and elastase activity. Change from baseline in the following outcomes at end of the treatment within patient and compared to placebo:

- 1. Plasma desmosine/isodesmosine (only change compared to placebo; withinindividual change is the primary outcome)
- 2. Plasma Aa-Val-360
- 3. Serum NE activity
- 4. Plasma proteinase 3
- 5. Plasma cathepsin B
- 6. Plasma CRP
- 7. Plasma IL-6
- 8. Plasma IL-8
- 9. Plasma IL-1b
- 10. Plasma RANTES
- 11. Plasma LTB4
- 12. Plasma MMP9
- 13. Plasma MMP12
- 14. Plasma MPO
- 15. Plasma PGP
- 16. Plasma PK/PD (LCG/DDS)

The above list was revised from the original protocol as a result of lack of data from sputum and BAL collections due to restrictions during the COVID pandemic. Data on NE may not be available on all subjects.

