#### 4. Objectives and Endpoints

Objective	Endpoint
Primary	

 
To evaluate the effect of alvelestat (MPH966) administered twice daily (bid) for 12 weeks on blood markers of neutrophil elastase activity
 
	
 
Within-individual % change from baseline in plasma desmosine/isodesmosine at end of treatment with MPH966
 

 
To evaluate the safety and tolerability of alvelestat (MPH966) administered twice daily (bid) for 12 weeks
 
	
 
Numbers and % of subjects who experience at least 1 treatment-emergent adverse event
 
Adverse events of special interest (liver function abnormalities, corrected QT interval/cardiac, infections, and neutropenia)
 

Secondary	

 
To evaluate the effect of alvelestat (MPH966) on other blood pharmacodynamic markers of neutrophil activation and elastase activity
 
	
 
Change from baseline in plasma desmosine/isodesmosine at end of treatment compared to placebo
 
Change from baseline in blood A<math>\alpha</math>-Val, NE, EL-NE, Proteinase 3, and Cathepsin B at end of treatment compared to placebo
 

 
To evaluate the effect of alvelestat (MPH966) on blood biomarkers of lung tissue degradation
 
	
 
Change from baseline in blood EL-CG, EL-P3, PGP, C6M, C1M, and PRO-C6, at end of treatment compared to placebo
 

 
To evaluate the effect of alvelestat (MPH966) on biomarkers of inflammation in blood
 
	
 
Change from baseline in blood high sensitivity C reactive protein, interleukin [IL]-6, IL-8, IL-1<math>\beta</math>, RANTES, fibrinogen, MMPs, and MPO at end of treatment compared to placebo
 

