# 3.2 Secondary Objectives

- To evaluate the effect of Alvelestat (MPH966) on other blood pharmacodynamic markers of neutrophil activation and elastase activity
- To evaluate the effect of Alvelestat (MPH966) on blood biomarkers of lung tissue degradation
- To evaluate the effect of Alvelestat (MPH966) on biomarkers of inflammation in blood

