# 10 Changes from Analysis Planned in the Protocol

In Version 1.3 of the protocol, augmentation therapy was removed from the list of not allowed treatment. Sample size calculation was revised but sample size remained the same. Also, stratified analyses by augmentation therapy will be performed.

Due to the risk during the COVID pandemic, spirometry as well as sputum and BAL collections were changed to optional. Consequently, all analyses using spirometry, sputum biomarkers, and BAL biomarker outcomes and data will no longer be performed in this study.

Primary analysis in the protocol is based on ANCOVA with outcome being the percent change at Week 12 from baseline. However, to minimize the effect of missing data and to maximize the information from all visits, the primary analysis is now based on fitting a mixed model using change from baseline at all available follow-up visits as outcome with the assumption of missing at random for missing data.

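### The SAP omits seven of the protocol's 20 blood secondary endpoints for a reason that fits only sputum and BAL, and keeps the lung-degradation objective with one of its six markers

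*SAP*

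**What the plan says.** Protocol Section 4 sets three secondary objectives on blood markers, each with named endpoints.

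- Neutrophil activation and elastase activity: plasma desmosine/isodesmosine (DES) against placebo, Aα-Val360, and "NE, EL-NE, Proteinase 3, and Cathepsin B at end of treatment compared to placebo".
- Lung tissue degradation: "Change from baseline in blood EL-CG, EL-P3, PGP, C6M, C1M, and PRO-C6, at end of treatment compared to placebo".
- Inflammation: hs-CRP, three interleukins, and "RANTES, fibrinogen, MMPs, and MPO at end of treatment compared to placebo".

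The biomarker table in Protocol 9.2.1 marks each of these for blood. It marks LTB4 for sputum and BAL only.

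SAP 3.2 keeps all three objectives, including "To evaluate the effect of Alvelestat (MPH966) on blood biomarkers of lung tissue degradation". SAP 4.3 then puts all 16 of its entries under a single description, "Blood pharmacodynamic markers of neutrophil activation and elastase activity", and gives this reason for the revision: "The above list was revised from the original protocol as a result of lack of data from sputum and BAL collections". Its only remark on availability of a blood marker is "Data on NE may not be available on all subjects", and that marker is kept. The title of SAP Table 1 also attributes its revision to removing sputum and BAL markers. SAP Section 10, which records departures from the protocol, says that "all analyses using spirometry, sputum biomarkers, and BAL biomarker outcomes and data will no longer be performed in this study". It names no blood marker.

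**The concern.** The reason given and the change made do not match. Failing to collect sputum or lavage fluid does not stop a marker being measured in plasma or serum, and both documents schedule biomarker blood at screening, at randomization and at Weeks 4, 8, 12 and 16.

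The make-up of the list matters here. SAP 6.6 makes no multiplicity adjustment, and SAP 8.2 reads each secondary outcome at p<0.05 as a treatment effect, so the markers on the list determine what can be claimed. Protocol 3.2 and 5.4 say that markers of inflammation and matrix breakdown will support the case for clinical benefit and feed the decision to progress.

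If the SAP is followed as written, seven prespecified endpoints go unanalysed with no applicable explanation. A conclusion on lung tissue degradation could also be reported from one marker, when six were planned, without Section 10 saying so.

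**Working it through.** No power or alpha figure is involved. The check compares the blood endpoints in Protocol Section 4 with SAP 4.3, and then with SAP 8.2, Table 1, 4.4 and Section 10.

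**Matching rules.** SAP serum NE activity is counted as carrying over protocol NE. SAP MMP9 and MMP12 together carry over protocol MMPs. SAP CRP carries over hs-CRP.

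| Protocol objective (blood) | Named | Kept in SAP 4.3 | Absent from SAP 4.3 |
|---|---|---|---|
| Elastase activity | 6 | DES, Aα-Val360, NE, proteinase 3, cathepsin B | EL-NE |
| Lung tissue degradation | 6 | PGP | EL-CG, EL-P3, C6M, C1M, PRO-C6 |
| Inflammation | 8 | CRP, IL-6, IL-8, IL-1β, RANTES, MMPs, MPO | Fibrinogen |
| Total | 20 | 13 | 7 |

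**Size.** Absent overall: 1 + 5 + 1 = 7, and 7/20 = 35%. Absent for degradation: 5/6 = 83%.

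**Reconciliation with the SAP count.** 20 − 7 = 13 protocol entries are kept. MMPs split into two gives 14. Adding plasma LTB4 and the PK/PD entry gives 16, which is the length of the SAP list.

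**Were the seven moved or explained elsewhere?**

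- SAP 8.2 and Table 1 carry the same 16 entries, without the seven.
- SAP 4.4 does not make them exploratory. By contrast, SAP 3.3 states openly that the lung-sample objective was moved to exploratory, and why.
- SAP Section 10 covers augmentation, the optional spirometry, sputum and BAL procedures, and the change from ANCOVA to a mixed model. It covers no blood marker, and not the addition of plasma LTB4.
- SAP 4.5.2 allows further markers to be run on stored samples, but this does not reinstate named endpoints.

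**Sensitivity to the matching rules.** If NE and NE activity are different analytes, the count becomes 8/20 = 40%, so seven is the conservative figure. MMP9 and MMP12 do not add to the degradation objective, because the protocol places MMPs under inflammation.

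**Sensitivity to how the SAP sentence is read.** If it is meant to explain only the sputum and BAL removals, the seven blood removals have no stated reason at all. The mismatch stands on either reading.

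**Outputs.** PGP has a figure in SAP 14.2 and appears in a listing in 14.3. In 14.1 the secondary efficacy tables, for both the Full Analysis Set and the Per-Protocol Set, end at MPO with no PGP table. The table list as read here is broken in one place, so this should be confirmed against the source file.

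**The case against.** The strongest reply is that this is an incomplete explanation in a signal-seeking study, touching neither the primary endpoint nor the power basis. Much of that stands, and it rules out several stronger readings that a reader might infer.

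- *Undeclared outcome switching.* SAP 4.3 says openly that its list differs from the protocol. Under SAP 3.6 investigators, participants, the manufacturer and the funder stay blinded until the end of the study, and under SAP 6.1 all analyses follow database lock. Nothing in the documents shows that markers were chosen on results. An assay or budget reason is possible; none is stated.
- *Blood was collected and results exist.* The schedules are plans, not collection records. They do not show which assays were run, failed or became unavailable.
- *Little evidence on elastin breakdown remains.* DES is kept, and Protocol 3.1 treats it as a useful marker of lung elastin degradation. Aα-Val360 is also kept, and both abbreviation lists define it as a product of elastase cleaving elastin. The protocol assigns both to the elastase-activity objective. What is lost is the collagen markers (C1M, C6M, PRO-C6), three further elastin markers (EL-NE, EL-CG, EL-P3) and fibrinogen.
- *NE was redefined.* The protocol's sputum and BAL endpoints name NE and NE activity separately, but its biomarker table has one NE row for all matrices. The SAP wording may be a clarification.
- *PGP will not be analysed.* SAP 8.2 commits to modelling it. A missing table would be a slip in the output list.

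The reply does not answer the mismatch itself: the stated reason does not apply to blood, and the section meant to record departures is silent.

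**Conclusion.** The concern holds as a protocol-to-SAP inconsistency with a limited but real effect on what can be concluded. Seven of 20 blood secondary endpoints (35%) are omitted without an applicable reason or a Section 10 entry. Plasma LTB4 is added without declaration. One objective is kept with one of its six protocol markers.

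The counts assume that serum NE activity continues blood NE and that MMP9 and MMP12 continue MMPs. They use the protocol's own grouping of markers by objective. The verdict makes no claim about motive or about whether samples or results exist.

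**What to change.** Before unblinding:

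1. Return to SAP 4.3, 8.2 and Table 1 any of EL-NE, EL-CG, EL-P3, C6M, C1M, PRO-C6 and fibrinogen for which blood results exist, and analyse them with the planned secondary model.
2. For the others, state the actual reason in Section 10 and list them as planned endpoints not measured. Limit the conclusion on the SAP 3.2 degradation objective to PGP, or to PGP plus whatever item 1 restores.
3. Label plasma LTB4 as added after the protocol, and say whether serum NE activity replaces or clarifies blood NE.
4. Add a PGP table to SAP 14.1 if it is in fact absent.

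Items 2 to 4 cost SAP wording and at most a PGP table. Item 1 costs some programming, for results already in hand. New assays on stored samples, which the documents allow to be kept for up to 60 months after the study ends, would need extra resources. They are optional and not part of the required fix.

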# 4.4 Exploratory Endpoints

- 1. Change from baseline in pre-and post-bronchodilator forced expiratory volume in 1 second (FEV1), forced vital capacity (FVC), FEV1/FVC (total and percent predicted), and maximal mid-expiratory flow at end of treatment. Data may not be sufficient to perform this analyses due lack of spirotmetry data.
- 2. Change from baseline in St. George's Respiratory Questionnaire (SGRQ) (overall and per domain), COPD Assessment Test (CAT), Modified Medical Research Council

Questionnaire (MMRC), San Diego Breath Questionnaire (SOBQ) and daily symptom scores

3. PK/pharmacodynamic (PD) relationship with efficacy biomarkers in blood and sputum. Due to the COVID pandemic, protocol was revised to make sputum collection optional. Only correlation of PK/PD with blood will be done.

# 4.5 Study Variables

### 4.5.1 Key Screening Assessments

### FIB-4 Score

The FIB-4 test combines age with 3 standard biochemical values (platelets, ALT, and AST) as a non-invasive test to assess fibrosis and enable exclusion of participants who may be at greater risk of liver AEs (https://www.mdcalc.com/fibrosis-4-fib-4-index-liver-fibrosis). The following formula will be used:

Using a cut-off value of 1.45, a FIB-4 score <1.45 has been shown to have a negative predictive value of 90% for advanced fibrosis. In contrast, a FIB-4 >3.25 would have a 97% specificity and a positive predictive value of 65% for advanced fibrosis. FIB-4 index has been shown to be superior to other scoring systems for differentiating between advanced and mild fibrosis.

# 4.5.2 Blood, Sputum, and Bronchoalveolar Lavage Biomarkers

### Blood

Blood will be collected as per the SOA, and samples will be collected and processed as described by the MOP.

### Sputum (this is optional due to COVID as reflected in the revised protocol Version 1.4)

Sputum will be collected from induced samples (refer to the MOP for processing details). Sputum induction will not be undertaken if the baseline  $FEV_1$  for the procedure is less than 1 L. Further details of sputum induction will be included in the MOP. Sputum induction is considered an aerosol generating procedure (AGP) and sites should use local guidance on conducting AGP as part of clinical research in the COVID-19 era.

# Bronchoalveolar Lavage (BAL) (this is optional due to COVID as reflected in the revised protocol)

BAL will be collected in the subset of participants who agree to participate in the bronchoscopy sub-study. Samples will be collected at two time points as per the SOA, and samples will be collected and processed as described by the MOP. Bronchoscopy and BAL is considered an aerosol generating procedure (AGP) and sites should use local guidance on conducting AGP as part of clinical research in the COVID-19 era.

Blood, sputum, and BAL efficacy biomarkers (see Table 1) will be taken at the time points as detailed in the SoA to evaluate their association with the observed mechanism of action responses to neutrophil elastase inhibition, including response of neutrophil elastase activity, inflammation, and lung damage to Alvelestat (MPH966).

The samples will be collected and processed as described in the MOP.

Samples may be stored for a maximum of 60 months following the end of study at a facility selected by the Sponsor to enable further analysis of biomarker responses to Alvelestat (MPH966).

Table 1	Biomarkers	of	Efficacy	Collected	in	Blood	(list	below	has	been	revised	to
exclude	biomarkers f	ron	n Sputun	n and BAL)								

Biomarker	Collected at Visit Number (see Figure 1 for week corresponding to visit number)
Plasma desmosine/isodesmosine	1, 3, 6, 8, 11, 12
Plasma Aa-Val-360	1, 3, 6, 8, 11, 12
Serum NE activity	1, 3, 6, 8, 11, 12
Plasma proteinase 3	3, 11
Plasma cathepsin B	3, 11
Plasma CRP	3, 11
Plasma IL-6	3, 11
Plasma IL-8	3, 11
Plasma IL-1b	3, 11
Plasma RANTES	3, 11
Plasma LTB4	3, 11
Plasma MMP9	3, 11
Plasma MMP12	3, 11
Plasma MPO	3, 11
Plasma PGP	1, 3, 11
Plasma PK/PD (LCG/DDS)	3, 4, 5, 6, 8, 9, 11, 12

In addition, samples will be stored and analysis may be performed on additional biomarker variants thought to play a role in neutrophil elastase–induced lung damage to evaluate their association with observed neutrophil activation responses to Alvelestat (MPH966).

Biomarker data are reported as concentration results, measured using a specific assay with a working range defined by the two limits: Lower limit of quantification (LLOQ) and Upper limit of quantification (ULOQ). Values which fall below the LLOQ or above the ULOQ are reported as <LLOQ \* dilution factor (dilution factor: if sample diluted and concentration measured still below LLOQ) and > ULOQ \* dilution factor, respectively. In case of censored values (values below the LLOQ and/or values above the ULOQ), the values, reported as <LLOQ will be imputed as 0.5\*LLOQ and values reported as >ULOQ will be imputed as 1.5\*ULOQ.

# 4.5.3 Functional and Quality of Life Instruments

#### • SGRQ-C

The St. George's Respiratory Questionnaire (SGRQ-C) will be administered at time points as detailed in the SoA. This is a questionnaire that measures health impairment in patients with COPD. It consists of 3 parts: a symptom score, an activity score, and an impact score. A total score is also produced.

#### • COPD Assessment Test (CAT)

The CAT is an 8 item questionnaire used to report health status in COPD. It will be administered at time points as shown in the SOA.

#### • Modified Medical Research Council (MMRC)

The MMRC will be administered at time points as detailed in the SoA and is used to measure dyspnea on a 5-point scale.

#### • San Diego Breath Questionnaire (SOBQ)

The SOBQ assesses patient reported dyspnea. The SOBQ will be administered at time points as detailed in the SoA.

#### • Pulmonary Function Testing/Spirometry

Pulmonary function testing (FEV1, FVC, FEV1/FVC, and maximal mid-expiratory flow) will be performed at the times specified in the SoA according to ATS guidelines. Further details on the spirometry procedure can be found in the Specific MOP. Spirometry is considered an aerosol generating procedure (AGP) and sites should use local guidance on conducting AGP as part of clinical research in the COVID-19 era.

### 4.5.4 Safety Assessments

Planned time points for all safety assessments are provided in the SoA.

#### • Physical Examinations

- A complete physical examination will include, at a minimum, assessments of the cardiovascular, respiratory, gastrointestinal, integumentary, and neurological systems. Height and weight will also be measured and recorded.
- A brief physical examination will include, at a minimum, assessments of the lungs, heart, abdomen, and skin indicating normal vs abnormal
- Investigators should pay special attention to clinical signs related to previous serious illnesses.

#### • Vital Signs

Vital signs will be measured in a semi-supine position after 5 minutes of rest and will include temperature, systolic and diastolic blood pressure, heart rate, respiratory rate, and pulse oximetry.

• Oral or tympanic temperature.

- Blood pressure and pulse measurements will be assessed with a completely automated device. Manual techniques will be used only if an automated device is not available.
- Blood pressure and pulse measurements should be preceded by at least 5 minutes of rest for the participant in a quiet setting without distractions (e.g., television, cell phones).
- Pulse oximetry will be measured using a sensor placed on the participant's fingertip or earlobe. Oxygen saturation (SpO2) will be recorded.

#### • Electrocardiograms

- 12-lead ECG will be obtained as outlined in the SoA using an ECG machine that automatically calculates the heart rate and measures PR, QRS, QT, and QTc intervals. Refer to the Protocol for QTc withdrawal criteria and additional QTc readings that may be necessary.
- Single ECGs will be performed at all scheduled time points, with the exception of when a change from baseline occurs that meets drug discontinuation criteria. In this situation, a triplicate measurement is required to confirm the finding and for discontinuation decisions.
- When a triplicate ECG is required, 3 consecutive ECG tracings should be taken in a 30-minute period with at least 5 minutes between each ECG.
- QTc value will be calculated using the Fridericia formula (QTc=QT/3 $\sqrt{RR}$ ).

#### Clinical Safety Laboratory Assessments

- The Investigator must review the laboratory report, document this review, and record any clinically relevant changes occurring during the study in the AE section of the CRF. The laboratory reports must be filed with the source documents. Clinically significant abnormal laboratory findings are those that are not associated with the underlying disease, unless judged by the Investigator to be more severe than expected for the participant's condition.
- All laboratory tests with values considered clinically significantly abnormal during participation in the study or within 28 days after the last dose of study treatment should be repeated until the values return to normal or baseline, with a frequency based on the judgement of the Site Investigator. If such values do not return to normal/baseline within a period of time judged reasonable by the Investigator, the etiology should be identified and the DCC notified.
- The monitoring schedule proposed for a case of acute liver function abnormalities or worsening of a liver function abnormality is reported is listed in the Protocol (Liver Test Abnormalities).
- Clinically significant liver function abnormalities should be reported as an AE/AESI.
- All protocol-required laboratory assessments must be conducted in accordance with the MOP and the SOA.

